**Pre-Screening and Baseline**

**Assessment.** The flow of participants through study procedures is summarized in Figure 3. Following initial recruitment by ALA counselors, potential participants will be contacted by research staff for a full study description and eligibility screening. The pre-screening questionnaire will be administered by phone. Those who remain interested and eligible, will complete informed consent remotely via a secure REDCap link sent by text message or email. Study staff will discuss the consent form while on the phone with the participant following the screening process. If the participant does not have time for this discussion, a second phone call will be arranged.

**Table 1. Study Conditions**

Condition	Education	Walking training	Inhaler training	Caregiver support
1	SHORT	ON	ON	ON
2	SHORT	ON	ON	OFF
3	SHORT	ON	OFF	ON
4	SHORT	ON	OFF	OFF
5	SHORT	OFF	ON	ON
6	SHORT	OFF	ON	OFF
7	SHORT	OFF	OFF	ON
8	SHORT	OFF	OFF	OFF
9	LONG	ON	ON	ON
10	LONG	ON	ON	OFF
11	LONG	ON	OFF	ON
12	LONG	ON	OFF	OFF
13	LONG	OFF	ON	ON
14	LONG	OFF	ON	OFF
15	LONG	OFF	OFF	ON
16	LONG	OFF	OFF	OFF

## PROTOCOL TITLE: COPD Helpline study

Consenting procedures will follow Rush IRB guidance for the use of electronic informed consent, described below.

Following consent, participants will be sent a baseline survey link by text message or email, or given the option to complete the baseline survey by phone interview format. After baseline survey completion, participants will be randomized to treatment following a randomization scheme programmed in REDCap. Participants will be mailed study materials specific to their treatment condition, consisting of the “Living Well with COPD” booklet and treatment material for up to three other treatment components.

Participants will be assigned to one of 16 possible experimental conditions, consisting of self-management education (either short or long duration) and up to three additional treatment components. The study schedule for each treatment condition is depicted in Figure 4. Self-management education will be delivered by an ALA Helpline counselor who is a certified COPD educator. Inhaler education will be delivered by a trained interventionist (advanced Respiratory Therapy student), overseen by the PI. Ground-based walking training and caregiver support will be delivered by a trained study staff member. All questionnaire assessments will be administered remotely through the REDCap data management system. Study staff will follow up with the participant to ensure all measures are completed, and address any questions or technical issues. Lastly, a subset of 15-20 participants will be invited to participate in a qualitative interview at end-of-treatment.

**Baseline Assessment (Week 0).** Prior to randomization, participants will complete a questionnaire battery of socio-demographic information, COPD-related measures, potential treatment mediators, and smoking-related measures, if applicable, as described below.

**Mid-treatment Assessment (Week 5).** Participants will complete a questionnaire battery of potential treatment mediators and adverse events, as described below.

[figure not shown]
**End-of-treatment Assessment (Week 8).**

Participants will complete a questionnaire battery of COPD-related measures, potential treatment mediators, and smoking-related measures, if applicable, as described below. Participants who were invited to participate in a qualitative interview will complete it at this stage.

[figure not shown]
**90-day follow up (Week 14).** Approximately 90 days after treatment start date, participants will complete a final questionnaire battery of COPD-related measures and smoking-related measures, if applicable, as described below.

**Intervention components.** Our selection of intervention components is based on recent, high-quality meta-analyses and international considerations: intervention components considered for inclusion in an optimized treatment package. Although patient education forms the ‘core’ of self-management treatment, education alone is insufficient to foster health behavior change. Instead, self-management treatment should be individually tailored and employ structured behavior change techniques.

**Figure 3. Study Procedures**

**Figure 4. Study Schedule for Each Treatment Condition**

## PROTOCOL TITLE: COPD Helpline study

Within multi-component programs, treatment components targeting physical activity are uniquely associated with improved health-related quality of life. Additionally, provision of social support is a critical component of COPD self-management treatment. Receiving positive social support from caregivers is consistently associated with improved health-related quality of life and self-efficacy among individuals with COPD. Overall, the four intervention components to be tested in the current study are supported by rigorous scientific evidence, relevant to a range of COPD stages, and can be combined with no conflict or redundancy in an optimized self-management intervention.

Self-management education duration (short vs. long). The self-management education condition is based on the Living Well with COPD program, which has been researched extensively. The program consists of a mailed booklet and structured phone counseling delivered by certified COPD educators. Topics include disease information, breathing retraining, action planning, medication use, energy conservation, and following good health habits. The ALA has offered the Living Well with COPD program to over 5700 callers with COPD since 2016.

The duration/ intensity of self-management education programs within the research literature is highly heterogeneous, ranging from a single session to 12 or more treatment contacts over up to 24 months. Although one meta-analysis found longer treatment duration to predict lower hospitalization risk, low-intensity treatments have demonstrated clinically significant effects on health-related quality of life and reduced hospitalization. Highly intensive treatment programs may also result in substantial treatment burden for individuals with COPD and limited scalability for population health. Thus, identifying optimal parameters of treatment intensity is critical. We will test a 2-session (short) versus 5-session (long) version of the self-management education program, in combination with the mailed booklet. The short condition consists of two calls (30-45 minutes each) to introduce patient education topics and refer to the booklet for further information. The long condition consists of five, weekly calls (30-45 minutes each) following a structured curriculum of patient education topics.

Ground-based walking training (GBWT; on vs. off). GBWT is a well-established, safe, and feasible physical activity program in COPD. As walking is the most common form of exercise undertaken in daily life, this modality allows for light to moderate intensity physical activity without the need for specialized equipment or professional supervision. Although long-term results are mixed, GBWT is associated with increased daily step count, exercise capacity, and quality of life and at 2- to 3-months. Participants randomized to this condition will be mailed a pedometer (3DFitBud Simple Step Counter) and instructed on its use to establish baseline steps/ day for 7 days. They will then receive a booklet with instructions to establish a walking program and three brief (10-15 minute), bi-weekly calls from a trained staff member to review step count values and engage in setting personal activity goals over the course of 6 weeks, following established exercise guidelines for individuals with COPD. Sessions will be conducted by phone or videoconference via a Zoom meeting hosted on a secure, HIPAA-compliant Rush Zoom account.

Inhaler education (on vs. off). Inhaled medications are commonly prescribed to manage COPD and prevent exacerbations. However, inhaler misuse is common, and errors in use are associated with worse symptoms and increased hospitalizations. Inhaler training with direct observation is shown to improve technique, but often not addressed in routine clinical care, representing a critical unmet need. Participants randomized to this condition will receive two sessions of inhaler technique education using a virtual teach-to-goal (TTG) method, in which individuals are observed using their inhaler, provided feedback, and then observed again. Sessions will be conducted by videoconference via a Zoom meeting hosted on a secure, HIPAA-compliant Rush Zoom account.

Caregiver support (on vs. off). Caregivers play a critical role in supporting quality of life among those with COPD, but frequently report unmet needs for support, disease information, and effective management strategies. Participants randomized to this condition will identify an informal caregiver who is involved in their healthcare (i.e., spouse, family member, or friend), who will receive a mailed copy of the Respiratory Health Association's COPD Caregiver's Toolkit, a comprehensive informational resource to support the care of the person living with COPD. Caregivers will receive two brief (10-15 minute) check-in calls from a trained staff member. The structured content of these sessions will include providing an overview of toolkit content,

## PROTOCOL TITLE: COPD Helpline study

identifying goals for sections(s) to review and incorporate into caregiving activities, and addressing any questions. Sessions will be conducted by phone or videoconference via a Zoom meeting hosted on a secure, HIPAA-compliant Rush Zoom account.

**Treatment fidelity.** The ability to deliver each intervention component, and combination of components, to fidelity is a key aspect of study feasibility. Checklists for each treatment condition will be created to describe both the necessary, and proscribed, elements of treatment. Following established procedures, we will use a rigorous database with embedded protocols to guide study activities and specify the order of implementation, such that participants receive all the intervention components to which they are assigned and only the intervention components to which they are assigned. Our study database will also include a scheduling program that tracks when research contacts occur and when visits or calls need to be scheduled based on the participants' condition.

### Measures.

#### Baseline characteristics.

Variables assessed at baseline include socio-demographics (i.e., age, gender, race/ ethnicity, employment status, and household income), medical history, and medication use. Health literacy will be assessed with the Calgary Charter on Health Literacy scale. COPD functioning will be assessed with the PROMIS Dyspnea-Activity Motivation scale; comorbid conditions will be assessed with the Charlson Comorbidity Index. For current cigarette smokers, we will assess baseline smoking characteristics with the Smoking History Questionnaire and nicotine dependence with the Heaviness of Smoking Index (HSI) and PROMIS-Nicotine Dependence scale.

#### Outcomes.

The primary outcome of health-related quality of life will be measured by the Chronic Respiratory Disease Questionnaire (CRQ), a 20-item questionnaire yielding a total score and subscale scores for mastery, fatigue, emotional functioning, and dyspnea. The total score ranges from 20-140, with 10 points considered to be a minimal clinically important difference. Secondary outcomes include COPD symptom burden, self-

Table 2. Measures	Timepoint Assessed			
	Baseline	Mid-treatment	End-of-treatment	90-day follow-up
COPD-related measures				
Chronic Respiratory Disease Questionnaire	X		X	X
COPD Assessment Test	X		X	X
Patient Activation Measure-13	X		X	X
Hospitalization history	X		X	X
PROMIS Dyspnea-Activity Motivation	X			
Charlson Comorbidity Index	X			
Medication Use	X			
Calgary Charter on Health Literacy scale	X			
Adverse events	X	X	X	X
Potential treatment mediators				
Bristol COPD Knowledge Questionnaire	X	X	X	
International Physical Activity Questionnaire	X	X	X	
Inhaler Confidence Scale	X	X	X	
PROMIS Informational Support	X	X	X	
Treatment acceptability				
Client Satisfaction Questionnaire			X	
Qualitative Interviews (subset of 15-20 ppts)				X
Smoking-related measures, if applicable				
Smoking History Questionnaire	X			
Heaviness of Smoking Index	X		X	X
PROMIS Nicotine Dependence	X		X	X

## PROTOCOL TITLE: COPD Helpline study

management behaviors, and hospitalization. COPD symptom burden will be assessed with the COPD Assessment Test (CAT), an 8-item questionnaire measuring the global impact of dyspnea on health status. Self-management behaviors will be assessed with the Patient Activation Measure (PAM-13), a 13-item questionnaire measuring patient knowledge, skill, and confidence for self-management. Self-reported hospitalization history will be assessed by asking participants if they have been hospitalized for their COPD (i.e., respiratory-related hospitalization) or other medical conditions (i.e., all-cause hospitalization) since enrolling in the study. Lastly, we will monitor for adverse events at all assessment timepoints, as described in the Data and Safety Monitoring Plan.

**Treatment mediators.** COPD knowledge will be assessed with the Bristol COPD Knowledge Questionnaire. Physical activity will be assessed with the International Physical Activity Questionnaire (IPAQ). Inhaler confidence will be assessed with the Inhaler Confidence Scale. Informational support will be assessed with the PROMIS Informational Support scale.

**Treatment acceptability.** We will assess treatment acceptability with the 8-item Client Satisfaction Questionnaire (CSQ-8), with adequate acceptability indicated by a total score of 24/30 or greater. To complement the CSQ-8, we will conduct qualitative interviews at end-of-treatment with a subset of approximately 15-20 participants, until thematic saturation is reached (i.e., the point at which each subsequent interview provides no new information). Qualitative interview content will focus on perceived benefits of treatment, treatment burden and other negative aspects of treatment, and suggestions for improving COPD self-management treatment. We will use a purposive sampling approach to ensure the sample is balanced by gender, race/ ethnicity, and exposure to each of the four treatment components. Following independent reviews of transcripts by the PI and trained research staff, and identification of *a priori* and in-vivo themes, initial codes will be assigned with content and comparative analysis using QSR NVivo version 11 software.

**Analytic Strategy.** Three main areas will be examined: 1. Feasibility of recruitment and outcome procedures. Feasibility will be evaluated via enrollment ratios, monthly recruitment rates, retention rates, and data completeness 2. Feasibility and acceptability of the treatment components. Treatment feasibility will be assessed by treatment fidelity ratings. Treatment acceptability will be assessed with the CSQ-8 in the full sample, and qualitative interviews in a subset of participants. 3. Explore the variability and acceptability of trial outcomes and treatment. We will examine the variability of the change in the COPD-related outcomes and treatment mediator measures. We will examine the proportion of hospitalization events over the course of the study, as well as the proportion of participants who endorse clinically meaningful change from baseline to 90-day follow-up on the CRQ and CAT. We will assess all questionnaires for good measurement properties (i.e., good internal consistency and sensitivity to treatment-related change) prior to selection in the planned optimization trial.

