## PROTOCOL TITLE: COPD Helpline study

### 1.0 Purpose of the Study:

Chronic Obstructive Pulmonary Disease (COPD) is an increasingly prevalent and costly chronic health condition, and is the third major cause of morbidity and mortality in the United States. Self-management treatment programs for COPD are shown to improve health-related quality of life and prevent COPD-related hospitalizations. Despite their clinical benefits, these programs are typically multi-component and time- and resource-intensive. To date, no study has been conducted to isolate the role of individual self-management treatment components in contributing to improved COPD outcomes. The proposed research will establish the feasibility of using the Multiphase Optimization Strategy (MOST) framework to optimize COPD self-management treatment delivered by the American Lung Association (ALA) Helpline. Treatment components to be evaluated include duration of self-management education, ground-based walking training, inhaler training, and caregiver support. The primary outcome is health-related quality of life, with secondary outcomes of COPD symptom burden, self-management behaviors, and hospitalization. Specific aims are:

**Aim 1: Design a factorial experiment and develop operational procedures.** We will design a factorial experiment with the same number of experimental conditions and length of follow-up as the planned optimization trial. In collaboration with the ALA COPD Helpline, we will develop operational procedures (i.e., recruitment, screening, randomization, and database management) for successful implementation.

**Aim 2: Establish feasibility and acceptability by pilot testing the study design.** We will deliver treatment to three participants per experimental condition ( $N=48$ ) with good fidelity, and will remotely assess baseline, mediator, and outcome variables. We will conduct qualitative interviews at end-of-treatment with 15-20 participants. Resulting values will provide estimates of recruitment and retention rates, treatment fidelity, acceptability of treatment components, and outcome measure variability to inform a subsequent, fully-powered optimization trial. The primary outcome is health-related quality of life, with secondary outcomes of COPD symptom burden, self-management behaviors, and hospitalization.

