**Monitoring of Data Quality**

The REDCap database will contain embedded protocols to guide study activities and specify the order of implementation, such that participants receive all the intervention components to which they are assigned and only the intervention components to which they are assigned. Quality assurance checks (i.e., required items, allowable ranges of response values) will be built into each REDCap survey to ensure data accuracy at the time of entry. Erroneous and/or inconsistent values will be flagged and entered into a recurring query report specifically developed for this study. Reports will be generated weekly and distributed to designated study staff for resolution. Once generated, a query will remain part of the weekly report until it is resolved. The PI will receive weekly aggregated reports on study recruitment and follow-up status and study intervention fidelity by treatment component. We will monitor the fidelity to the treatment protocol timeline and percentage of components delivered in each treatment condition. Our study database will also include a scheduling program that tracks when research contacts occur and when visits or calls need to be scheduled based on the participants' condition.

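### Does the CSQ-8 acceptability criterion need changing because a maximum of 30 does not fit eight items and the summary unit is left open?

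*Combined protocol and SAP*

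**What the plan says.** Section 4.0, Measures, Treatment acceptability, names the instrument and its criterion: "the 8-item Client Satisfaction Questionnaire (CSQ-8), with adequate acceptability indicated by a total score of 24/30 or greater". The paragraph then adds a second source of evidence: "To complement the CSQ-8, we will conduct qualitative interviews at end-of-treatment with a subset of approximately 15-20 participants".

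Section 4.0, Analytic Strategy, says the CSQ-8 will be assessed in the full sample. It names no mean, median or proportion. For two other scales the same paragraph does name a participant-level summary: "the proportion of participants who endorse clinically meaningful change from baseline to 90-day follow-up on the CRQ and CAT".

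Section 4.0, Outcomes, gives the range of the 20-item CRQ: "The total score ranges from 20-140". No comparable range is given for the CSQ-8.

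Section 1.0, Aim 2, explains what the pilot is for: "Resulting values will provide estimates of recruitment and retention rates, treatment fidelity, acceptability of treatment components", among other quantities, to inform a later, fully powered trial. Section 14.0, Monitoring of Data Quality, adds: "Quality assurance checks (i.e., required items, allowable ranges of response values) will be built into each REDCap survey".

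**The concern.** There are two grounds for concern, both in one sentence.

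The item count and the denominator do not fit together. Eight items scored alike in whole numbers cannot reach a maximum of exactly 30. A reader who takes 24/30 as 80% of the maximum may have the wrong idea of how demanding the criterion is. That reader may also wonder whether the intended rule is a raw 24 or 80% of the true maximum.

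The unit of the criterion is also open. A sample mean of 24 and a requirement that most participants reach 24 are different standards, and the plan does not choose between them or give a required proportion.

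This is the plan's only numeric criterion for acceptability, and acceptability is one of the quantities the pilot hands on to the optimization trial. The stake would be an acceptability claim that is misdescribed, or one whose summary is chosen after the scores are seen.

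**Working it through.** **Inputs from the documents.** CSQ-8 items: 8. Criterion: 24, printed over 30 (both Section 4.0, Treatment acceptability). CRQ: 20 items, total 20 to 140 (Section 4.0, Outcomes). Planned sample: 48 (Section 4.0, Participants). The CSQ-8 item range is not given anywhere.

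**1. Can the printed maximum be reproduced?** For k items on a common scale with top score m, the maximum is k × m. Setting 8 × m = 30 gives m = 30/8 = 3.75, which is not a whole number. So 30 is not reproduced under equal whole-number scoring. The same check works for the CRQ: 140/20 = 7 and 20/20 = 1, which is a 1-to-7 item scale.

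**2. What does this rest on?** Equal scoring and whole-number scoring are both assumptions. Unequal item ranges or a rescaled total could give 30. The plan describes neither, but it does not rule them out.

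**3. Is the cut-off affected?** 24/8 = 3.0 per item, so 24 is attainable whenever the top item score is at least 3. Only its expression as a percentage moves:

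| Top item score (assumed) | Maximum | 24 as % of maximum |
|---|---|---|
| 3 | 8 × 3 = 24 | 24/24 = 100% |
| 4 | 8 × 4 = 32 | 24/32 = 75% |
| 5 | 8 × 5 = 40 | 24/40 = 60% |

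The printed ratio is 24/30 = 80%. If the top item score is 4 and 80% were the real intention, the cut-off would be 0.8 × 32 = 25.6, that is, 26. The sentence states the rule as a total score, however, not as a percentage.

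**4. How far apart are the mean and participant readings?** Assume near-normal whole-number scores with SD 3 to 5. The share at 24 or above, with a half-point correction, is 1 − Φ((23.5 − mean)/SD). For example, with mean 24 and SD 3: 1 − Φ(−0.5/3) = 0.566.

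| Assumed mean | SD 3 | SD 4 | SD 5 |
|---|---|---|---|
| 24 | 0.566 | 0.550 | 0.540 |
| 25 | 0.691 | 0.646 | 0.618 |
| 26 | 0.798 | 0.734 | 0.691 |
| 28 | 0.933 | 0.870 | 0.816 |

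When the mean sits on the threshold, a little over half of participants reach it, as any roughly symmetric distribution would give. At a mean of 28, between 82% and 93% reach it. No row shows a changed decision, because the plan sets no required proportion against which the participant reading could fail.

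**5. Does anything downstream use either quantity?** The Analytic Strategy lists enrollment ratios, monthly recruitment, retention, data completeness and fidelity ratings, all without numeric targets. It contains no hypothesis test on the CSQ-8 and no rule for going on to the optimization trial that depends on it.

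**The case for a change.** The strongest case for a change is that it is nearly free. One sentence could give the item range, the maximum and the unit, with no added visit, assessment or payment. Stating the unit in advance would also stop the team from choosing whichever of the mean and the proportion looks better. The contrast within the Analytic Strategy supports this, since the plan names a proportion of participants for the CRQ and CAT but not for the CSQ-8. The survey checks in Section 14.0 would not settle the matter. They apply to response values, and the documents do not say that they fix a total-score maximum or correct the protocol text.

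Part of this stands. The item count and the 30 do not fit under ordinary scoring, and the unit is not stated. The rest does not carry enough weight. A total score most naturally belongs to one respondent, so the sentence already has an ordinary reading. The missing required proportion is in keeping with a pilot that sets no numeric target for any of the feasibility measures in its Analytic Strategy. A favourable choice of summary would gain little, because both summaries can be reported side by side from the same scores, and the interviews provide separate evidence. The 24-or-26 question arises only if the denominator is read as defining the rule, and nothing in the documents supports that reading over the stated total of 24.

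**Conclusion.** No change to the plan follows. Under equal whole-number scoring of eight items, 30 cannot be the maximum (30/8 = 3.75), so the denominator is probably a clerical slip. It is not a proven one, because the documents give no CSQ-8 scoring rule. The cut-off of 24 is explicit, attainable and not shown to be wrong. Correcting the 30 would move only a descriptive percentage, from 80% to 75% if the top item score is 4 (an assumption), and would alter no analysis or conclusion.

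The open unit is a gap in a descriptive pilot that an analyst fills sensibly by reporting the mean together with the share of participants at 24 or above. The calculated differences between the two readings rest on an assumed near-normal shape, assumed SDs and assumed means, and are largest when the mean lies at the threshold. They show no changed decision.

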**Participants.**

[figure not shown]
The randomized factorial experiment will consist of 48 participants. We will partner with the American Lung Association (ALA) Illinois chapter team and recruit participants from the ALA COPD Helpline for this study, following recruitment procedures described below. The PI has collaborated with the ALA-Illinois chapter team since 2015, and the proposed research is a natural extension of this partnership. As the ALA Living Well with COPD programs reaches over 800 callers per year, we believe that accrual targets (4 participants/ month; planned N=48) will be feasible in the grant period.

**Procedures.** We will conduct a pilot randomized factorial trial in which participants will be randomized to one of two levels for each of the four intervention components. This will result in a total of 16 study conditions, 3 participants per condition (N=48).

**Length of participation.** As shown in Figure 4, participants will be enrolled in the study for approximately 4 months (14 weeks).

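### Acceptability data will come only from people still responding at Week 8, and the interview sampling does not seek early stoppers, so acceptability may be overstated

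*Combined protocol and SAP*

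**What the plan says.** Aim 2 (section 1.0 of the combined protocol and SAP) lists acceptability among the quantities the pilot must supply for the later optimization trial. The Analytic Strategy in section 4.0 states: "Treatment acceptability will be assessed with the CSQ-8 in the full sample", with interviews in a subset. The Treatment acceptability paragraph sets a criterion, "adequate acceptability indicated by a total score of 24/30 or greater", but does not say whether it applies to the mean score or to each participant.

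In Table 2 the row "Client Satisfaction Questionnaire" has one mark, under end-of-treatment, which section 4.0 places at Week 8. The Week 5 contact has no acceptability measure: "Participants will complete a questionnaire battery of potential treatment mediators and adverse events".

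For the interviews, "we will conduct qualitative interviews at end-of-treatment with a subset of approximately 15-20 participants, until thematic saturation is reached". Selection uses a "purposive sampling approach to ensure the sample is balanced by gender, race/ ethnicity, and exposure to each of the four treatment components". The interview topics include burden and other drawbacks of treatment. Table 2 marks the interviews under 90-day follow-up while the text places them at end of treatment. The two must be reconciled, but both fall at or after Week 8.

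The document gives no expected retention, no rule for a missing CSQ-8 score, and no questionnaire or interview for people who leave early.

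**The concern.** A person who leaves before Week 8 contributes no CSQ-8 score and is unlikely to be interviewed. If people leave because the programme is a burden, both acceptability measures miss the least satisfied, and both err in the same direction.

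This matters because burden differs by design. From the component descriptions in section 4.0, condition 9 has 5 education calls, 3 walking calls, 2 inhaler sessions and 2 caregiver calls, or 12 contacts (two of them with the caregiver). Condition 8 has 2 calls. The rationale for testing education duration itself warns that intensive programmes can burden patients. Loss could therefore differ by component, and scores from responders alone could fail to show which component people find hard to accept. The optimization trial needs that information from the pilot.

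**Working it through.** **Planned sample.** Four two-level components give 2^4 = 16 conditions, and 16 × 3 = 48, as stated. Each level of a component has 8 × 3 = 24 people.

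**Proportion meeting the CSQ-8 criterion.** Let m of the 48 have no score, p_R be the proportion meeting the criterion among responders, and p_N the proportion among the missing. Then

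p_all = [(48 − m) p_R + m p_N] / 48, and overstatement = p_R − p_all = (m/48)(p_R − p_N).

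The document gives none of m, p_R or p_N. Assume p_R = 85%, p_N = 85%, 60% or 40%, and 10%, 20% or 30% missing (5, 10 or 14 people). For example, with m = 14 and p_N = 40%: (34 × 0.85 + 14 × 0.40)/48 = 34.5/48 = 71.9%, an overstatement of 13.1 points. The bounds count all missing as failing, (48 − m) p_R / 48, or all as meeting the criterion, [(48 − m) p_R + m] / 48.

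| Missing | p_all (overstatement), p_N = 85% | p_N = 60% | p_N = 40% | Bounds |
|---|---|---|---|---|
| 5 | 85.0% (0) | 82.4% (2.6) | 80.3% (4.7) | 76.1-86.6% |
| 10 | 85.0% (0) | 79.8% (5.2) | 75.6% (9.4) | 67.3-88.1% |
| 14 | 85.0% (0) | 77.7% (7.3) | 71.9% (13.1) | 60.2-89.4% |

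The upper bounds exceed 85%: if the missing were more satisfied than responders, the error would run the other way.

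**Mean score.** The overstatement is (m/48) × (difference in means). If the missing score 3 to 6 points lower (assumed), it runs from 5/48 × 3 = 0.31 to 14/48 × 6 = 1.75 points.

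**By component.** Suppose 6 of 24 are missing with a component on and 2 of 24 with it off, again with 85% and 40%. Responders show 85% at both levels. Among all randomized the figures are (18 × 0.85 + 6 × 0.40)/24 = 73.8% and (22 × 0.85 + 2 × 0.40)/24 = 81.3%, a difference of 7.5 points that the responders' scores do not show.

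**Interviews.** If k interviewees were drawn at random from all 48, the chance of including none of m early stoppers is C(48 − m, k)/C(48, k).

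| Early stoppers | Expected in 15-20 interviews | Chance of none, k = 15 | k = 20 |
|---|---|---|---|
| 5 | 1.6-2.1 | 14% | 6% |
| 10 | 3.1-4.2 | 1.4% | 0.2% |
| 14 | 4.4-5.8 | 0.2% | 0.01% |

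These chances assume that every stopper can still be reached at Week 8 or later. For those lost to the study that does not hold.

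**The case against.** Much of the opposing case stands.

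- A reader might infer that the *full sample* phrase contradicts Table 2. It does not. In context it contrasts asking everyone with interviewing a subset, and it does not promise complete response.
- A reader might infer that people who stop treatment are excluded at Week 8. The document does not say so. The assessment is a scheduled remote survey, staff chase incomplete measures (section 4.0), and payment depends on completing the assessment (section 12.0), not on staying in treatment.
- A reader might infer that acceptability will be biased upward. The document gives no dropout rate and no link between loss and satisfaction. People may also be lost through illness or technical problems.
- Sampling error is of similar size. At 85% of 48, the standard error is sqrt(0.85 × 0.15/48) = 5.2 points, or about ±10 points at 95%. No go/no-go rule is tied to the criterion. This limits the consequence, but a confidence interval shows sampling error and does not show error from missing responders.
- Retention, data completeness and delivery by component are monitored (Analytic Strategy; section 14.0), so attrition will be visible. Those data show how many left and from which condition, not how acceptable they found the treatment.
- Nothing bars early stoppers from interview, and exposure could mean exposure received. Even so, the frame does not require any to be included.
- Exit scores would be taken at a different time and exposure from Week 8 scores, and a fixed interview quota has no stated basis: at 10% stopping there would be only about 5 such people. Both points shape the fix.

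**Conclusion.** The point holds as a cheap improvement, not as a flaw that invalidates the pilot. Acceptability will describe those still responding at Week 8. It may be biased upward if loss to assessment is related to dissatisfaction or burden. The documents do not support saying that it will be.

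The size is unknown. The range of 0 to about 13 percentage points rests on assumed inputs: 10-30% of 48 missing, 85% of responders meeting the criterion, and 40-85% of the missing meeting it. It is zero if nobody is missing or if the missing resemble responders. It applies only to people lost to assessment, not to everyone who stops a component.

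**What to change.** 1. Add stopping early or missing assigned sessions to the purposive sampling frame. Invite such participants when they stop, and include some of them within the planned 15-20 interviews, without a fixed quota.
2. Send the existing CSQ-8 REDCap link at withdrawal from the study as well as at Week 8, and report the exit scores separately from the Week 8 scores.
3. Report CSQ-8 results with the number scored out of all randomized, overall and at each level of each component, with bounds that count the missing scores as all below and all at or above the criterion.

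The cost is one extra REDCap trigger, a changed invitation rule and a few added lines in the report. The number of interviews does not change. Some who leave will not reply, and exit scores will not be directly comparable with Week 8 scores, which is why they are kept apart.
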